# 5.5. Subject Withdrawal, Termination, and Replacement

Study subjects may discontinue from the study or be withdrawn from the study for any of the following reasons:

- At the subject's or the subject's legally authorized representative with the subject's assent request for any reason (withdrawal of consent)
- Subject whose cognitive function declines and is deemed by the Investigator to be unable to provide assent/consent for continuation in the study
- At the discretion of the Investigator, if deemed appropriate, for any reason
- At the discretion of the Sponsor, if deemed appropriate, for any reason
- Subject for whom investigator deems initiation of memantine medically necessary must be withdrawn
- Subject noncompliance: If a subject takes less than 70% of study drug tablets, this may be considered reason for withdrawal, by Investigator or Sponsor request
- Protocol violation that compromises subject safety
- For safety concerns; medically significant AE(s) or SAE(s) with CTCAE > Grade 3 may be considered reason for withdrawal, if appropriate in the judgment of the Investigator
- Subject who becomes pregnant must be withdrawn from the study
- The subject's caregiver/study partner is no longer willing or able to participate in the study and a suitable replacement caregiver/study partner cannot be found
- Brain MRI findings: subject who has any of the following findings on central reading:
  - o Macrohemorrhage: defined as hemorrhage with size > 1 cm^3
  - o ARIA-E (vasogenic edema) associated with neurologic symptoms: dosing will be halted for 1 month and MRI repeated. Resumption of dosing may be considered after discussion between Investigator and Sponsor's medical officer.
- Subject who experiences an event of syncope without a clear triggering event (e.g., blood draw or pain inducing a vasovagal episode) will be withdrawn from the study
- Subject with clinically notable ECG abnormalities based on the average of triplicate ECG readings. The criteria for clinically notable or significant ECG results that require subject withdrawal are as follows:
  - o QTcF (Fridericia's correction) interval > 500 msec, and
  - An increase in QTcF interval of > 60 msec from baseline.

Confidential Page 51 of 115

**Note:** The criteria for QTcF are based on the upper threshold in elderly subjects who are known to have higher ULN [Reardon & Malik, 1996], and is the threshold commonly used in AD studies.

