4.2 Exploratory Imaging Biomarker Outcomes

MRI Sub-study: All subjects will be included in the MRI sub-study with serial imaging at baseline, 26, 52 and 78 weeks; approximately 250 of the 300 enrolled subjects are expected to provide MRIs at the final Week 78 visit. For total hippocampal volume (HV), reduction of HV atrophy of ~20% may be expected with ALZ-801. This is based on tramiprosate Phase 3 data that suggested significant reduction of HV atrophy over 78 weeks (Gauthier 2009). In addition, the Phase 3 study of lecanemab (Van Dyck 2023) showed significant reduction of HV atrophy of ~8% over 78 weeks. No formal statistical powering was conducted for this exploratory outcome.

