8.1.4 Handling of Multiple Observations

For clinical efficacy data, if multiple measures were recorded for the same protocol defined visit, the later (repeated) measure will be used for data summary and analysis. Repeated data from unscheduled visits will be treated similarly.

If a subject has a scheduled visit, the assessment obtained at the scheduled visit will be used for data summary and analysis. Otherwise, if no scheduled visit assessment exists but at least one unscheduled visit assessment is available within the protocol-defined visit window, then the data at the latest unscheduled visit within the protocol-defined visit window will be used for data summary and analysis. Furthermore, in cases where both an unscheduled visit assessment and an early terminated visit assessment exist within the same analysis window, the assessment from the early terminated visit will be utilized for summarization and analysis.

When a subject undergoes multiple scheduled MMSE screening measurements, the most recent assessment will be used as the screening score. Any previous records showing MMSE scores below 22 should be regarded as instances of screen failure.

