8.2.1 Visit Windows

Data at scheduled visits will be assigned to analysis visits as defined in the Analysis Visit Window tables below (Table 2, Table 3, Table 4, Table 5, Table 6, Table 7), to ensure that all visits have the potential to be included in the summaries. The unscheduled visits on or before day 1 will be mapped according to scheduled assessments. Visit windows herein will also be used to classify unscheduled and early termination visits.

For volumetric MRI measures (vMRI), if multiple measures were recorded for the same protocol defined visit, the later (repeated) measure will be used for data summary and analysis. If vMRI measures are missing for a protocol defined visit and an unscheduled vMRI measure is available, the unscheduled vMRI measure will be mapped to the closest missing protocol defined visit.

Table 2 Analysis Visit Windows for Assessments Done at Visit 4, 5, 7, 8, 9, 10, 11

Stage/Visit	Target Day	Study Days	
		Lower Bound	Upper Bound
Week 6 (Visit 4)	43	2	67

Stage/Visit Target Day		Stud	y Days
Week 13 (Visit 5)	92	68	137
Week 26 (Visit 7)	183	138	228
Week 39 (Visit 8)	274	229	319
Week 52 (Visit 9)	365	320	410
Week 65 (Visit 10)	456	411	501
Week 78 (Visit 11)	547	502	592

Table 3 Analysis Visit Windows for Assessments Done at Visit 5, 7, 8, 9, 10, 11

Stage/Visit	Target Day	Study Days	
		Lower Bound	Upper Bound
Week 13 (Visit 5)	92	2	137
Week 26 (Visit 7)	183	138	228
Week 39 (Visit 8)	274	229	319
Week 52 (Visit 9)	365	320	410
Week 65 (Visit 10)	456	411	501
Week 78 (Visit 11)	547	502	592

Table 4 Analysis Visit Windows for Assessments Done at Visit 4, 5, 7, 9, 11

Stage/Visit	Target Day	Study Days	
		Lower Bound	Upper Bound
Week 6 (Visit 4)	43	2	67
Week 13 (Visit 5)	92	68	137
Week 26 (Visit 7)	183	138	274
Week 52 (Visit 9)	365	275	456
Week 78 (Visit 11)	547	457	592

Table 5 Analysis Visit Windows for Assessments Done at Visit 5, 7, 9, 11

Stage/Visit	Target Day	Study Days	
		Lower Bound	Upper Bound
Week 13 (Visit 5)	92	2	137
Week 26 (Visit 7)	183	138	274
Week 52 (Visit 9)	365	275	456
Week 78 (Visit 11)	547	457	592

Table 6 Analysis Visit Windows for Assessments Done at Visit 7, 9, 11

Stage/Visit	Target Day	Study	y Days
		Lower Bound	Upper Bound
Week 26 (Visit 7)	183	2	274
Week 52 (Visit 9)	365	275	456
Week 78 (Visit 11)	547	457	592

Table 7 Analysis Visit Windows for Assessments Done at Visit 9, 11

Stage/Visit	Target Day	Study Days	
		Lower Bound	Upper Bound
Week 52 (Visit 9)	365	2	456
Week 78 (Visit 11)	547	457	592

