8.5.3 Evaluation of ARIA on Brain MRI

Evaluation of amyloid-related imaging abnormalities or ARIA on Safety MRIs (Sperling 2011) will include evaluation of ARIA-E (brain edema or effusion), ARIA-H (microhemorrhages), ARIA-H (superficial siderosis) and ARIA-H (macrohemorrhages). Safety MRIs will also be analyzed for severity of white matter disease (WMD) in the periventricular and deep white matter, using the Fazekas severity scores. Other ischemic abnormalities such as lacunes or infarcts will also be evaluated. Shift tables for the 4 types of ARIA, WMD parameters and the other ischemic lesions will be provided by visit. Continuous variables for the ARIA-H will also be summarized by visit.

Drug Suspension due to MRI Findings

Some subjects who develop MRI findings of interest may be instructed to suspend study drug till resolution of the MRI finding. The number of subjects whose study drug was suspended by the Sponsor or investigator for MRI finding, and the reason for study drug suspension [ARIA-

E or ARIA-H with macrohemorrhage or ARIA-H with siderosis, or a combination of these lesions)] will also be summarized.

Clinical Laboratory Evaluations

Clinical lab results will be reported for hematology, clinical chemistry, coagulation tests, and urinalysis and will be summarized by visit.

Parameters will be summarized descriptively through change from baseline (CFBL) and percent CFBL for numeric values. If a parameter is categorical, it will be listed only.

Out-of-range values will be assessed through shift tables. Each lab value will be assessed as low, normal or high based on the normal ranges provided by the central lab. Frequencies of each combination of shifts will be provided.

Potentially clinically significant (PCS) tables will also be used to summarize out-of-range values. Summaries will be given for any time post-baseline. The denominator for the percentages will be the number of patients with a result at the specific visits for each parameter.

All laboratory results will be listed, including scheduled and unscheduled/repeat measurements (if any). Laboratory assessments that are outside of normal ranges and/or with potential clinical significance will be flagged in the listings.

Clinically notable changes in LFTs will be summarized and listed for individual study subjects. The criteria for clinically significant LFT results are as follows:

- ALT $> 5 \times ULN$,
- AST $> 5 \times ULN$, or
- $TBL > 3 \times ULN$

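### SAP 8.2.1 moves an unscheduled vMRI to the nearest missing visit with no day limit, against the analysis windows in the same section and with no stated precedence

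*SAP*

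**What the plan says.** SAP 4.2 sets the imaging schedule: "All subjects will be included in the MRI sub-study with serial imaging at baseline, 26, 52 and 78 weeks". The windows that match it are in SAP Table 6 ("Analysis Visit Windows for Assessments Done at Visit 7, 9, 11"):

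- Week 26: target Day 183, Days 2 to 274
- Week 52: target Day 365, Days 275 to 456
- Week 78: target Day 547, Days 457 to 592

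Three statements in SAP 8.2.1 bear on an unscheduled scan.

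- The general paragraph: "Visit windows herein will also be used to classify unscheduled and early termination visits".
- The first vMRI sentence: where several measures exist for one protocol visit, the later one is used.
- The second vMRI sentence: "If vMRI measures are missing for a protocol defined visit and an unscheduled vMRI measure is available", then "the unscheduled vMRI measure will be mapped to the closest missing protocol defined visit".

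No order of precedence is given. By contrast, SAP 8.1.4, which opens with clinical efficacy data, keeps the scheduled assessment if there is one. Otherwise it takes unscheduled data only where "at least one unscheduled visit assessment is available within the protocol-defined visit window".

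**The concern.** The vMRI rule looks for the closest visit that is missing, not the closest visit. A nearer visit that already has a scan is skipped, and nothing limits how far the scan may then be moved. Hippocampal volume is expected to fall with time, so the shift has a direction. A scan moved to a later visit shows too little atrophy, and one moved to an earlier visit shows too much.

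The analysis does not correct for this. The model in SAP 8.4.1 is an MMRM by visit, and its listed terms do not include scan date. If Week 78 were left missing, the likelihood-based model would handle it under missing at random, as SAP 8.3.1 describes for the primary endpoint. The mapping instead supplies a mis-dated number as an observed Week 78 value. The slope analysis, which could use actual dates, is optional (SAP 8.3.2).

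Unscheduled scans are foreseeable. For ARIA-E with neurologic symptoms, Protocol 5.5 says "dosing will be halted for 1 month and MRI repeated". SAP 8.5.3 adds: "Some subjects who develop MRI findings of interest may be instructed to suspend study drug till resolution of the MRI finding". Protocol 7.1.10.6 uses post-dose MRIs for both safety and volumetry. Subjects with such scans are selected on an MRI finding and may be off drug, so they need not be balanced between arms.

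**Working it through.** **Reproducing the plan's figure.** Protocol 10.3.3 assumes 125 per arm, a difference of 68 mm³, SDs of 165 (drug) and 147 (placebo), two-sided α = 0.05, and claims more than 90% power.

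- Average SD: s = √((165² + 147²)/2) = 156.3 mm³.
- Power = Φ(68/(156.3 × √(2/125)) − 1.96) = Φ(3.44 − 1.96) = 0.931. This agrees with the protocol.

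**Where the scans land.** Targets are Days 183, 365 and 547.

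| Scan day | Visits with a scan | Missing visit | Literal vMRI rule | Table 6 window |
|---|---|---|---|---|
| 395 | Weeks 26, 52 | Week 78 | Week 78, 547 − 395 = 152 days early | Week 52 |
| 300 | Weeks 52, 78 | Week 26 | Week 26, 300 − 183 = 117 days late | Week 52 |

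Day 395 is also 457 − 395 = 62 days before the Week 78 lower bound. If Week 26 is missing as well, Day 395 still goes to Week 78 (152 days away against 212). If Week 52 is missing, it goes correctly to Week 52 (30 days away).

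**Error in one record.** Assume linear loss over Days 1 to 547 at the protocol's placebo rate: 6% of 3100 = 186 mm³ over 546 days.

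- Day 395 recorded as Week 78: 186 × 394/546 = 134 mm³ instead of 186, which is 52 mm³ too little. Against the protocol SDs this is 52/165 = 0.31 to 52/147 = 0.35.
- Day 300 recorded as Week 26: 186 × 299/546 = 102 mm³ instead of 186 × 182/546 = 62, which is 40 mm³ too much.

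In the drug arm the protocol's assumed loss is 186 − 68 = 118 mm³, so the Day 395 error is 118 × 152/546 = 33 mm³. Day 395 is an illustration, not a ceiling, because the rule has no bound.

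**Effect on the trial.** The affected shares are assumptions; the documents give none.

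| Share with a Day 395 scan as Week 78 | Active arm only, 118 mm³ loss: spurious benefit | Active arm only, no drug effect (186 mm³ loss): spurious benefit | Both arms equally: difference (power) |
|---|---|---|---|
| 2% | 0.7 mm³ | 1.0 mm³ | 67.6 mm³ (0.928) |
| 5% | 1.6 mm³ | 2.6 mm³ | 67.1 mm³ (0.924) |
| 10% | 3.3 mm³ | 5.2 mm³ | 66.1 mm³ (0.917) |

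The one-arm columns are share × loss × 152/546. The last column is 68 × (1 − share × 152/546). If 17% of both arms were affected, as many as the protocol's projected drop-outs, the difference would be 64.8 mm³ and power 0.906.

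**The case against.** The best defence is that the section can be read another way. If the windows apply first, the Day 395 scan is a Week 52 scan. The repeat-measure sentence then treats it as a second Week 52 value, and Week 78 stays missing. That reading is tenable, so it cannot be said that the plan will turn a Day 395 scan into Week 78, only that its literal wording does. The defence does not remove the problem. The section supports two different datasets, and under the window reading an unscheduled scan replaces the scheduled Week 52 scan.

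The route is also narrow. It needs an evaluable unscheduled vMRI, a filled nearer visit and a missing later one. The early termination visit includes an MRI (Protocol 7.2.14), and the windows classify such visits, so some missing Week 78 values will be filled properly. Protocol 2.4 reports no ARIA-E on active drug among 426 subjects with central MRI readings in the tramiprosate Phase 3 studies. SAP 8.5.3 mentions drug suspension, not an extra scan. All of this limits the likely frequency, which remains unknown.

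A reader might set the 52 mm³ error beside the 68 mm³ the protocol sought (52/68 = 76%), or beside the SAP's expected reduction of about 20% (0.20 × 186 = 37 mm³; 52/37 = 139%), and conclude that the effect could be swamped. That compares one subject's error with a difference between group means, and the documents do not support the inference.

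**Conclusion.** The defect is real and limited. SAP 8.2.1 holds two unreconciled rules. The more specific one, read literally, has no day limit and enters mis-dated volumes as observed. Under linear 6% loss from 3100 mm³, the illustrative Week 78 record is wrong by about 52 mm³, a third of an SD. At trial level the bias is about 1 to 5 mm³ if 2 to 10% of one arm alone is affected. If both arms are affected equally, the result is slight attenuation.

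A reader might infer that the rule manufactures apparent preservation of volume on drug. The documents do not support that. Scans can be moved backwards as well as forwards, and if the placebo arm were the one affected at Week 78 the bias would work against the drug. Nothing shows which arm would have more such scans.

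No confirmatory result depends on this. Hippocampal volume was the primary imaging endpoint in the protocol, but it is exploratory in SAP section 5, has no formal powering in SAP 4.2 and lies outside the testing procedure in SAP 8.1.5. The reason to act is that the ambiguity is easy to remove beforehand and awkward to settle once results are known.

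**What to change.** Replace the second vMRI sentence in SAP 8.2.1, before unblinding, with a rule that states three things:

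1. An unscheduled vMRI fills a missing visit only if its study day lies within that visit's Table 6 window.
2. Where a scheduled scan exists in that window, it is kept. For unscheduled scans this takes precedence over the repeat-measure sentence.
3. All other unscheduled scans are listed and used only in the optional slope model, at their actual dates.

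The cost is a short text change and the loss of a few out-of-window scans from the by-visit MMRM. Some timing error remains because the Table 6 windows are wide. A Day 457 scan still counts as Week 78, 90 days early (186 × 90/546 = 31 mm³). A Day 2 scan could count as Week 26, 181 days early (186 × 181/546 = 62 mm³). The change therefore bounds the error and makes the dataset reproducible, but it does not eliminate the error.

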8.2.2 Handling of Missing Data for Safety and AE

- Missing baseline values for vital signs, laboratory tests, ECG and safety MRIs will not be imputed..
- Missing post-baseline values for by-visit data will be summarized using the Visit Windows from Appendix 1. If a value is not available within a given window, no imputation will be done.
- Missing data for Adverse Event (AE) relationship will be imputed as "Related."
- Missing data for AE stop or start dates are imputed as follows:
 - o If the imputed stop date precedes the start date (whether imputed or non-imputed), the imputed stop date will be adjusted to match the start date.
 - If the stop date is complete and the imputed start date falls after the stop date, then the start date will be imputed using the stop date.
 - Incomplete dates for AEs or non-study medications, the missing component(s) will be assumed as the most conservative database and shown in the data listings.
 - o If AE is ongoing, the end date will not be imputed.
- Rules for partial dates are described in Table 8 below.

Table 8 Missing Date Imputation Rules

Parameter	Missing	Additional Conditions	Imputation
Start date for AEs	Time only		Time will not be imputed; but
			will be assumed to be after 1st
			dose date
	D only	M and Y same as M and Y of first	Date of first dose
		dose date	
		M and/or Y not same as M and Y	First day of non-missing month
		of first dose date	
D and M		Y same as Y of first dose date	Date of first dose
		Y not same as Y of first dose date	Use January 1 of non-missing
			year
	M, D and Y	None – date completely missing	Date of first dose
Stop date for AEs	Time only		Time will not be imputed
	D only		Last day of non-missing month
	D and M		Use Dec 31 of non-missing year
	M, D and Y	Deceased	Date of death

Parameter	Missing	Additional Conditions	Imputation
		Not deceased	Date of the end of trial
			participation
Start date for	D only	M and Y same as M and Y of first	Date of first dose
Concomitant		dose date	
medications		M and/or Y not same as M and Y	First day of non-missing month
		of first dose date	
	D and M	Y same as Y of first dose date	Date of first dose
		Y not same as Y of first dose date	Use January 1 of non-missing
			year
	M, D and Y	None – date completely missing	Date prior to date of first dose
Stop date for	D only	M and Y same as M and Y of first	Last day of non-missing month
Concomitant		dose date	
medications		M and/or Y not same as M and Y	Last day of non-missing month
		of first dose date	
	D and M	Y same as Y of first dose date	Use Dec 31 of non-missing year
		Y not same as Y of first dose date	Use Dec 31 of non-missing year
	M, D and Y	None – date completely missing	Date will not be imputed

8.2.3 Handling of Missing Efficacy Data

- Missing baseline values of efficacy scales will not be imputed in any situation.
- Missing post-baseline values for by-visit data will be summarized and analyzed based on the mappings to Visit Windows (Section 8.2.1). Sensitivity analysis will be conducted to evaluate the impact of missing efficacy data (total score) as detailed in Section 8.3.

8.2.4 Efficacy Data Algorithms and Handling of Missing Sub-Items or Domains in Calculating Total Scores

If any of the individual sub-items for the primary or secondary endpoints is missing, the total score of the corresponding endpoint will be imputed by prorating the observed scores (van Ginkel 2010). The criteria for imputations are specific for each scale, as defined below.

ADAS-Cog 13/ ADAS-Cog 11: The ADAS-Cog 13 consists of 13 items for a score range of 0-85, and the ADAS-Cog 11 consists of 11 of the 13 items for a score range of 0-70, where higher scores indicate more severe cognitive deficits (Table 9).

For ADAS-Cog 13, if 3 or fewer of 13 items (<25%) are missing, the total score will be imputed by the following algorithm: ADAS-Cog 13 Total Score = Total score from the completed items × [maximum total score (=85) / maximum total score corresponding to the completed items]. The imputed number will be derived and rounded up to the nearest two decimal places. If more than 3 items are missing, the total score of ADAS-Cog 13 at that visit will be considered missing.

For ADAS-Cog 11, if 2 or fewer of 11 items (<25%) are missing, the total score will be imputed by the following algorithm: ADAS-Cog 11 Total Score = Total score from the completed items × [maximum total score (=70) / maximum total score corresponding to the completed items]. The imputed number will be derived and rounded up to the nearest two decimal places. If more than 2 items are missing, the total score of ADAS-Cog 11 at that visit will be considered missing.

Table 9 ADAS-Cog 13 and 11 Items and Algorithm for derivation of Item Scores and Total Score

Item	Algorithm	Range
Word Recall	Total number of "No" responses. Subscore is the sum the scores from	0-10
	trials 1, 2, and 3, divide by 3.	
Commands	Total number of "No" responses from 5 tasks	0-5
Constructional Praxis	Count number of "No" responses. Subscore is 0=all 4 drawings correct;	0-5
	1=1 figure drawn incorrectly; 2=2 figures drawn incorrectly; 3=3 figures	
	drawn incorrectly; 4=4 figures drawn incorrectly; 5=no figures drawn,	
	scribbles, parts of forms	
Naming Objects /	Total number of "No" responses. Subscore is 0= 0-2 "no" responses;	0-5
Fingers	1=3-5 "no" responses; 2=6-8 "no" responses; 3=9-11 "no" responses	
	4=12-14 "no" responses; 5=15-17 "no" responses	
Ideational Praxis	Total number of "No" responses.	0-5
Orientation	Total number of "No" responses.	0-8
Word Recognition	Total # of "1" responses. If total is 12 or less, trial score=total. If total is	0-12
	>12, trial score=12.	
Remembering Test	Subscore is 0=None, 1=Very Mild, 2=Mild, 3=Moderate, 4=Moderately	0-5
Instruction	Severe, 5=Severe	
Comprehension	Subscore is 0=None, 1=Very Mild, 2=Mild, 3=Moderate, 4=Moderately	0-5
	Severe, 5=Severe	
Word Finding	Subscore is 0=None, 1=Very Mild, 2=Mild, 3=Moderate, 4=Moderately	0-5
Difficulty	Severe, 5=Severe	
Spoken Language	Subscore is 0=None, 1=Very Mild, 2=Mild, 3=Moderate, 4=Moderately	0-5
	Severe, 5=Severe	
Number Cancellation	Adjusted Score = Total # correct targets crossed off minus Total #	0-5
(included in ADAS-	incorrect targets crossed off minus Total # times reminded of task. Then	
Cog 13)	use Adjusted Score to determine subscore as follows; Adjusted Score	
	Subscore ≥23=0; 18-22=1; 13-17=2; 9-12=3; 5-8=4; ≤4=5	
Delayed Word Recall	Total number of "No" responses.	0-10
(included in ADAS-		
Cog 13)		
ADAS-Cog 13 Total	Sum of 13-item scores	0-85
ADAS-Cog 11 Total	Sum of 11-item scores without "Number Cancellation" or "Delayed	0-70
	Word Recall"	

A-IADL: A-IADL consists of 47-70 items and is a scale administered to informant aimed at detecting deficits in instrumental and complex functions at the early stages of AD (Sikkes 2013). These activities include, but are not limited to, cooking, doing finances, and shopping. They are complex everyday tasks, determined by multiple cognitive processes and controlled processing (Dubbelman 2022a; Teng 2023). The A-IADL score can be determined using item

response theory (IRT) method (A-IADL-IRT, Sikkes 2013) or the weighted average method (A-IADL-W, Teng 2023).

A-IADL-IRT has a score range of 20-80 and will be calculated and transferred from a third party vendor for categorical responder analysis (Dubbelman 2022a). A-IADL-W has a score range of 0-100 and is calculated as follows: (sum of all scores / number of questions scored) × 25 which will be used for secondary efficacy analysis (Table 10, Teng 2023). For A-IADL-IRT, higher scores indicates better functioning, while for A-IADL-W, higher scores indicates worse functioning or more impairment.

If <25% (11 or fewer of 47; or 17 or fewer of 70 questions are answered) are answered as "don't know", A-IADL-W will be derived without imputation and considered valid. If the scores from more than 11 items are not available, A-IADL-W at that visit will be considered missing.

Table 10 A-IADL Algorithm for derivation of Total Score

Algorithm

If Yes is selected in main question with performance level:

No = 0

Yes, slightly more difficult = 1

Yes, more difficult =2

Yes, much more difficult =3

Yes, he/she is no longer able to perform this task =4

If No is selected in main question with performance level:

He/she was no longer able to do so due to cognitive problems = 4

He/she was no longer able to do so due to physical problems = Not scored

He/she has never done that before = Not scored

Other, please state = Not scored

A-IADL-W = (sum of all scores / number of questions scored) \times 25

CDR-SB: The CDR consists of 6 boxes for a score range of 0-18 (Table 11). It is a global rating scale used to assess the stage and severity of dementia (Morris 1993). It uses a structured, clinician-rated interview that collects information on cognitive and functional capacity from both the subject and caregiver. Higher score on CDR-SB indicates more advanced AD.

The CDR-SB will be determined by adding the individual scores from each of the six domains. The same imputation technique will be applied to missing CDR-SB boxes or sub-items. If only 1 of 6 boxes (<25%) of the CDR is missing, the sum of the boxes will be imputed by prorating the sum from the other 5 boxes: CDR-SB Total Score = Total score from the completed items × [maximum total score (=18) / maximum total score corresponding to the 5 completed boxes (=15)]. The imputed number will be derived and rounded up to the nearest integer. If more than 1 box is missing, the total score of CDR-SB at that visit will be considered missing.

CDR-G: The CDR scale also provides a derived global score (CDR-G) which indicates disease stage, with CDR-G= 0 indicating no impairment, CDR-G= 0.5 indicating MCI, CDR-G=1

indicating Mild AD, and CDR-G = 2 or 3 indicating Moderate and Severe AD, respectively. CDR-G scale will be used for categorical responder analyses. In the event of a single missing box score on the CDR-SB, the aforementioned imputed CDR-SB score can be used to derive CDR-G score.

Table 11 CDR Items and Algorithm for derivation of Item Scores and Total Score

Item	Algorithm	Range
Memory	0=normal, 0.5=questionable; 1=mild, 2=moderate, 3=severe	0-3
Orientation	0=normal, 0.5=questionable; 1=mild, 2=moderate, 3=severe	0-3
Judgment and Problem Solving	0=normal, 0.5=questionable; 1=mild, 2=moderate, 3=severe	0-3
Community Affairs	0=normal, 0.5=questionable; 1=mild, 2=moderate, 3=severe	0-3
Home and Hobbies	0=normal, 0.5=questionable; 1=mild, 2=moderate, 3=severe	0-3
Personal Care	0=normal/questionable, 1=mild, 2=moderate, 3=severe	0-3
CDR-SB Total	Sum of all items	0-18

MMSE: The MMSE is a measure of global cognition that is widely used for clinical staging of AD (Folstein 1975). It consists of 11 domains items for a score range of 0-30 to assess general cognitive function (Table 12). Higher score on MMSE means better cognitive skills.

The same imputation algorithm will be applied to the MMSE. If 2 or fewer of 11 domains (<25%) of the MMSE are missing, the total score will be imputed by prorating the sum from the other completed domains: MMSE Total Score = Total score from the completed domains × [maximum total score (=30) / maximum total score corresponding to the completed domains]. The imputed number will be derived and rounded up to the nearest integer. If the scores from more than 2 domains are not available, the MMSE at that visit will be considered missing. For MMSE, higher total scores indicate better cognition.

Table 12 MMSE Domains and Algorithm for derivation of Domain Scores and Total Score

Domain	Algorithm	Range
Orientation to Time	5 questions: Total number of "Correct" answers	0-5
Orientation to Place	5 questions: Total number of "Correct" answers	0-5
Registration	3 words: Total number of "Correct" answers	0-3
Calculation	5 questions: Total number of "Correct" answers	0-5
Recall	3 words: Total number of "Correct" answers	0-3
Naming	2 questions: Total number of "Correct" answers	0-2
Repetition	1 question: Total number of "Correct" answer	0-1
Comprehension	3 questions: Total number of "Correct" answers	0-3
Reading	1 question: Total number of "Correct" answer	0-1
Writing	1 question: Total number of "Correct" answer	0-1
Drawing	1 question: Total number of "Correct" answer	0-1
MMSE Total	30 questions: Total number of "Correct" answers	0-30

DAD: The DAD consists of 40 items with a score range of 0-100 to evaluate the basic and instrumental activities in daily activities of subjects with dementia (Gélinas 1999). It is administered through an interview with the caregiver (Table 13). Higher DAD scores indicate less disability or better function.

DAD Total Score is calculated as follows: (DAD Total / DAD Number of Applicable Items) × 100. If 2 or fewer of 10 items (<25%) of the DAD are missing, the DAD Total Score will be derived without imputation and considered valid. If the scores from more than 2 items are not available, the DAD Total Score at that visit will be considered missing.

Table 13 DAD Items and Algorithm for derivation of Item Scores and Total Score

Item	Algorithm	Range
Hygiene	7 questions: Total number of "Yes" answers	0-7
Dressing	5 questions: Total number of "Yes" answers	0-5
Continence	2 questions: Total number of "Yes" answers	0-2
Eating	3 questions: Total number of "Yes" answers	0-3
Meal preparation	3 questions: Total number of "Yes" answers	0-3
Telephoning	4 questions: Total number of "Yes" answers	0-4
Going on an Outing	5 questions: Total number of "Yes" answers	0-5
Financing and Correspondence	4 questions: Total number of "Yes" answers	0-4
Medications	2 questions: Total number of "Yes" answers	0-2
Leisure and housework	5 questions: Total number of "Yes" answers	0-5
DAD Total	40 questions: Total number of "Yes" answers	0-40
DAD Number of Applicable Items	Sum of Applicable Items	0-40
DAD Total Score	(DAD Total / DAD Number of Applicable Items)×100	0-100

NPI-12: Early AD patients may experience various neuropsychiatric symptoms that emerge and worsen with disease progression and contribute to the morbidity and healthcare burden of AD (Forester 2019). The NPI assesses the neuropsychiatric or behavioral symptoms of AD, including their frequency and severity (Cummings 1997). It is a self-administered questionnaire completed by caregivers about subjects for whom they care. The NPI-12 has 12 sub-items, each item has score range of 0-12 with a NPI-total score range of 0-144 for subject's symptoms and 0-60 for caregiver distress (Table 14). Higher scores on each NPI sub-item indicate more severe or frequent occurrence of that symptom. Higher scores on NPI-12 indicate more severe burden of neuropsychiatric or behavioral symptoms.

The same imputation algorithm will be applied to the NPI-12 and Caregiver Distress. If 2 or fewer of 12 items (<25%) of the NPI-12 are missing, the total score will be imputed by prorating the sum from the other completed items: Total score = total score from the completed items × [maximum total score (=144) / maximum total score corresponding to the completed items]. If 2 or fewer of 12 items (<25%) of the Caregiver Distress are missing, the total Caregiver Distress score will be and derived and imputed by prorating the sum from the other completed items: Total Caregiver Distress score = total score from the completed items × [maximum total score (=60) / maximum total score corresponding to the completed items].

The imputed number will be rounded up to the nearest integer. If the scores from more than 2 items are not available, the NPI-12 at that visit will be considered missing.

Table 14 NPI-12 Items and Algorithm for derivation of Item Scores and Total Score

Item	Algorithm	Range	Caregiver Distress Range
Delusions	Frequency (0-4), Severity (0-3)	0-12	0-5
Hallucinations	Frequency (0-4), Severity (0-3)	0-12	0-5
Agitation/Aggression	Frequency (0-4), Severity (0-3)	0-12	0-5
Depression/Dysphoria	Frequency (0-4), Severity (0-3)	0-12	0-5
Anxiety	Frequency (0-4), Severity (0-3)	0-12	0-5
Elation/Euphoria	Frequency (0-4), Severity (0-3)	0-12	0-5
Apathy/Indifference	Frequency (0-4), Severity (0-3)	0-12	0-5
Disinhibition	Frequency (0-4), Severity (0-3)	0-12	0-5
Irritability/Lability	Frequency (0-4), Severity (0-3)	0-12	0-5
Aberrant Motor Behavior	Frequency (0-4), Severity (0-3)	0-12	0-5
Sleep	Frequency (0-4), Severity (0-3)	0-12	0-5
Appetite Disorder	Frequency (0-4), Severity (0-3)	0-12	0-5
NPI-12 Total	Sum of all items	0-144	0-60

QoL-AD: The QoL-AD consists of 13 items for a score range of 13-52 for participant (subject) and informant (cargiver or study partner) (Logsdon 2002, Table 15), where higher scores indicate better quality of life.

The same imputation algorithm will be applied to the QoL-AD participant and informant. If 3 or fewer of 13 items (<25%) of the QoL-AD are missing, the total score will be imputed by prorating the sum from the other completed items: Total score = total score from the completed items × [maximum # of items (=13) / (# of completed items)]. The imputed number will be rounded up to the nearest integer. If the scores from more than 3 items are not available, the QoL-AD at that visit will be considered missing.

Table 15 QoL-AD (Participant and Informant) Items and Algorithm for derivation of Item Scores and Total Score

Item	Algorithm	Range
Physical Health	Poor (1), Fair (2), Good (3), Excellent (4)	1-4
Energy	Poor (1), Fair (2), Good (3), Excellent (4)	1-4
Mood	Poor (1), Fair (2), Good (3), Excellent (4)	1-4
Living Situation	Poor (1), Fair (2), Good (3), Excellent (4)	1-4
Memory	Poor (1), Fair (2), Good (3), Excellent (4)	1-4
Family	Poor (1), Fair (2), Good (3), Excellent (4)	1-4
Marriage	Poor (1), Fair (2), Good (3), Excellent (4)	1-4
Friends	Poor (1), Fair (2), Good (3), Excellent (4)	1-4
Self as a Whole	Poor (1), Fair (2), Good (3), Excellent (4)	1-4
Ability to Do Chores Around the House	Poor (1), Fair (2), Good (3), Excellent (4)	1-4
Ability to Do Things for Fun	Poor (1), Fair (2), Good (3), Excellent (4)	1-4
Money	Poor (1), Fair (2), Good (3), Excellent (4)	1-4
Life as a Whole	Poor (1), Fair (2), Good (3), Excellent (4)	1-4
QoL Total	Sum of all items	13-52

RUD Lite: The RUD Lite consists of two sections related to the caregiver and to the subject (Wimo 2013). In particular, the following reported hours/minutes or reported events will be listed and summarized by treatment and by baseline MMSE using descriptive statistics. Missing data will be left blank without imputation.

- Caregiver sleep time (hours and minutes) in the last 30 days
- Caregiver time (hours and minutes) and number of days in the last 30 days in assisting subject with tasks in toilet visits, eating, dressing, grooming, walking and bathing
- Caregiver time (hours and minutes) and number of days in the last 30 days in assisting subject with tasks in shopping, food preparation, housekeeping, laundry, transporation, taking medication, and managing financial matters
- Caregiver time (hours and minutes) and number of days in the last 30 days in supervising the subject to prevent dangerous events
- Number of times the subject is admitted in a hospital (for more than 24 hours) since last visit
- Number of times the subject is admitted in a hospital emergency room (for less than 24 hours) since last visit

